# Estimating the Cumulative Distribution of a Right-Censored Counterfactual Outcome, Accounting for Informative Censoring

To accommodate informative censoring due to drop-out from a health plan, switching to an alternate medication, or discontinuation of study medication, IPCWs will be estimated. Specifically, a linear-logistic model for the conditional probability of remaining uncensored  $Pr(\Delta_i=1|D_i, A_i)$ , where  $D_i$  is a vector of measured confounders of drop-out / switching / discontinuation and the outcome and  $A_i$  is a discrete random variable denoting exposure to erenumab-aooe (a=1) or other mAbs targeting the CGRP pathway (a=0) for patient i, will be fit. IP censoring weights will then be constructed as:

$$\widehat{W}_i^2 = \frac{1}{\widehat{Pr}(\Delta_i = 1 | D_i, A_i)}$$

Variables to be included in the censoring model will include demographic characteristics, medication usage, disease history, and utilization of medical resources, all of which will be included in the censoring model (see Appendix D). For new users of erenumab-aooe and other mAbs targeting the CGRP pathway, the cumulative incidence curves weighted

by inverse probability of censoring weights provide a valid estimate of the risk for acute MI at various time points, now accounting for informative censoring.

The cumulative incidence curves for acute MI, weighted by the multiple of IPTWs (ie,  $\widehat{W}_i^1$ ) and IPCWs (ie,  $\widehat{W}_i^2$ ), account for both confounding by measured covariates and informative censoring. The full estimating function for the counterfactual cumulative incidence of acute MI is then defined as:

$$\widehat{Pr}(T^a < t) = \frac{1}{n} \sum_{i=1}^{n} \frac{\Delta_i I(T_i < t) I(A_i = a)}{Pr(\Delta_i = 1 | D_i, A_i) \Pr(A_i = a | L_i)}$$

### Modeling Assumptions

Results from these analyses will be subject to limitations if certain assumptions of the methods are violated. The assumptions include the following:

- i. Conditional exchangeability, given measured covariates
- ii. No misclassification of the exposure, outcome, or other study variables
- iii. Stable unit treatment value assumption (SUTVA), which requires that outcomes are not correlated
- iv. Consistency, such that exposures can be mapped to well-defined interventions
- v. Positivity, wherein there are at least some exposed and unexposed individuals at each level of the confounders
- vi. No misspecification of the three models considered in these analyses: (a) the structural (ie, weighted) model, (b) the exposure model (ie, the PS model), and (c) the censoring model(s).

Discussion of the impact of violations of these assumptions are deferred to later sections.

# 8.7.2.5 Sensitivity Analysis

# 8.7.2.5.1 Subgroup Analysis

Not applicable.

# 8.7.2.5.2 Stratified Analysis

The cumulative incidence for all three CV outcomes (hypertension, acute MI, stroke) will be stratified by prior history of cardiovascular disease (defined as the occurrence of any of the following events during the baseline period: ischemic stroke, hemorrhagic stroke, unspecified stroke, transient ischemic attack, subarachnoid hemorrhage, intracerebral hemorrhage, other acute cerebrovascular events, other ischemic cerebrovascular events, acute myocardial infarction, myocardial ischemia, congestive heart failure, acute

ventricular tachycardia, acute atrial fibrillation, paroxysmal atrial fibrillation, acute ventricular fibrillation, premature atrial contractions, Prinzmetal angina, unstable angina pectoris, other and unspecified angina pectoris, coronary revascularization, peripheral artery disease, or venous thromboembolism), by prior history of risk factors for cardiovascular disease, including hyperlipidemia, diabetes, and hypertension, and by migraine aura. In addition, the cumulative incidence of acute MI, and, separately, the cumulative incidence of stroke will be stratified by prior history of hypertension only.

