#### 6.2 Rationale

CGRP is a neuropeptide that is expressed in the central and peripheral nervous systems and has been implicated in migraine pathophysiology. In addition, CGRP can mediate vasodilation (Russell et al, 2014) and, therefore, inhibition of the CGRP pathway might result in cardiovascular effects, such as increased blood pressure; however, vasodilatory pathways are redundant, and the relative importance of the CGRP pathway compared with the other vasodilatory pathways (eg, nitric oxide) has not been established. CGRP and its receptors are also found in blood vessels and in the heart (Favoni et al, 2019). Clinical trials evaluating CGRP mAbs for migraine prevention have shown no imbalance in CV adverse events, including hypertension, between active medication and placebo groups. Moreover, during the development of erenumab-aooe, a number of dedicated clinical and nonclinical studies were conducted to address a theoretical cardiovascular risk, and collectively these studies support the cardiovascular safety of erenumab-aooe (Kudrow et al, 2020).

During the fourth quarter of 2019, the FDA identified hypertension as a potential adverse drug reaction (ADR) for erenumab-aooe. On 30 April 2020, new onset hypertension and exacerbation of existing hypertension were added to the Warning and Precautions section of the USPI for erenumab-aooe. In addition, because the phase 2 and 3 clinical trials for erenumab-aooe had a limited number of subjects (0.5%) enrolled with preexisting cardiovascular (CV) disease (Dodick et al, 2018; Goadsby et al, 2017, Tepper et al, 2017), use of erenumab-aooe in patients with major CV disease (including acute myocardial infarction [MI] and stroke) is classified as missing information in the Core Risk Management Plan for erenumab-aooe.

In this study, the risk of hypertension, acute MI, and stroke will be estimated in the following four new user cohorts: erenumab-aooe, other mAbs targeting the CGRP pathway, select standard of care (SOC) migraine preventive medications (anti-epileptics), and onabotulinumtoxinA. Also, if appropriate based on comparability analyses, the relative risk (RR) of acute MI and stroke will be separately estimated for the following three comparisons: (1) erenumab-aooe vs. other mAbs

targeting the CGRP pathway, (2) erenumab-aooe vs. select SOC migraine preventive medications (anti-epileptics), and (3) erenumab-aooe vs. onabotulinumtoxinA.

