### 8.2.2.1 Inclusion Criteria

Patients must meet the following inclusion criteria:

- 1. 18-64 years of age on the index date.
- 2. One year of continuous enrollment (ie, complete medical and pharmacy coverage) prior to and including the index date, which defines the baseline period.
- 3. A diagnosis of migraine during the baseline period, based on one of the following criteria:
  - a) ≥1 inpatient claim with a diagnosis of migraine (ICD-10-CM) diagnosis code of G43.xxx).
  - b) ≥1 outpatient evaluation and management claim with a diagnosis of migraine and a specialty code of 260 (neurologist).
  - c)  $\geq 1$  claim for emergency room visit with a diagnosis of migraine.
  - d) ≥1 outpatient evaluation and management claim with a diagnosis of migraine PLUS ≥1 pharmacy fill for a migraine-specific triptan or an ergotamine class medication within 365 days of each other
  - e) ≥2 outpatient evaluation and management claims with a diagnosis of migraine between 7 and 365 days apart.
  - f) ≥2 pharmacy fills for migraine-specific triptans or ergotamine class medications between 7 and 365 days apart.

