#### 8.2.4 Baseline Period

The index date for all medication cohorts is the earliest prescription claim date for a given medication occurring during the study period that satisfies the inclusion/exclusion criteria. The 365 days of continuous enrollment (ie, complete medical and pharmacy coverage) prior to and including the index date will be the baseline period.

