### **Descriptive Analyses**

### Estimating the Cumulative Distribution of a Right-Censored Outcome

Following the notation by Cole et al (Cole et al, 2015) and Brookhart (Brookhart, 2019), let  $T_i$  be the continuous random variable for the time from treatment initiation to acute MI

for the  $i^{th}$  patient, and let *t* represent the realization (ie, a specific value) of  $T_{i.}$  The cumulative incidence (ie, risk) of the acute MI outcome at time *t* is the complement of the Kaplan-Meier survival function,

$$R(t)=1-S(t)=\Pr(T_i < t).$$

The entire function over time is of interest, but the cumulative incidence of acute MI at times t=6 months, t=1 years, and t=2 years after the start of treatment will also be estimated.

The naïve, unadjusted cumulative incidence of the outcome, R(t), subject to rightcensoring by *C*, can be conveniently estimated with the following estimating function:

$$\widehat{Pr}(T < t) = \frac{1}{n} \sum_{i=1}^{n} \frac{\Delta_i I(T_i < t)}{Pr(\Delta_i = 1)},$$

where  $\Delta = l(T < C)$  is an indicator that the patient was uncensored. In the denominator  $Pr(\Delta_i = 1)$  implies that censoring is non-informative (ie,  $C \perp T$ ), and, so, the cumulative incidence curve that is initially estimated assumes that censoring occurs at random.

In addition to estimating the cumulative incidence, the incidence rate, overall, and by selected baseline characteristics, with 95% confidence intervals based on the Poisson distribution, will also be estimated.

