Acute ventricular fibrillation	Х	Х	С	
Premature atrial contractions	Х	Х	С	
Acute ventricular tachycardia	Х	Х	С	
Coronary revascularization	Х	Х	С	
Ischemic/hemorrhagic stroke	Х	Х	С	
Sub-arachnoid stroke	Х	Х	С	
Unspecified stroke	Х	Х	С	
Transient ischemic attack	Х	Х	С	
Other acute cerebrovascular events	Х	Х	С	
Other ischemic cerebrovascular events	Х	Х	С	

Page 4 of 4

a Additional variables predictive of treatment assignment or censoring may be added to the respective models, based on identification of the most common diagnoses, procedures, and medications identified in the study population.

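### The cardiovascular-history stratum covers only the last 365 days and names no history codes, so an unknown share of older MI and stroke patients is classed as having no history

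*Protocol*

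**What the plan says.** Section 8.7.2.5.2 stratifies hypertension, acute MI and stroke by "prior history of cardiovascular disease (defined as the occurrence of any of the following events during the baseline period". The list that follows has 22 items. Some are acute events. Others can be continuing conditions: it includes "acute myocardial infarction, myocardial ischemia, congestive heart failure" and ends with "coronary revascularization, peripheral artery disease, or venous thromboembolism".

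The window is fixed in two places that agree. The inclusion criteria (8.2.2.1) require "One year of continuous enrollment (ie, complete medical and pharmacy coverage) prior to and including the index date, which defines the baseline period". Section 8.2.4 says: "The 365 days of continuous enrollment (ie, complete medical and pharmacy coverage) prior to and including the index date will be the baseline period". No longer look-back is given anywhere.

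Table 1 and Appendix D use largely the same labels. Appendix D, for example, lists "Ischemic/hemorrhagic stroke" alongside acute myocardial infarction and transient ischemic attack, all assessed in the baseline period. None of the three lists has an item for old MI, personal history of stroke or TIA, or cerebrovascular sequelae. An earlier MI or stroke is not an exclusion (8.2.2.2).

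**The concern.** The label speaks of history; the definition counts what was recorded in one year. A patient with a stroke 13 months before index and no listed code since goes into the no-history stratum, and the stroke indicator in the treatment model is 0. A patient with premature atrial contractions coded in the past year goes into the history stratum, because that item is listed.

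This matters because of the study's own rationale. Section 6.2 notes that few trial subjects had pre-existing cardiovascular disease (0.5%), and that use in patients with major cardiovascular disease, MI and stroke included, "is classified as missing information in the Core Risk Management Plan for erenumab-aooe". The stratification by cardiovascular history is the planned analysis closest to that gap. Patients with an established but older MI or stroke belong to the population of interest, and the definition can place them in the contrasting stratum. The same omission removes the direct indicator of an older event from the propensity score and censoring models.

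Section 8.9 does not mention it. Section 8.9.1.1 deals with exposure measurement and 8.9.1.4 with smoking, while the modeling assumptions in 8.7.2.4 require that study variables are not misclassified.

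**Working it through.** The plan gives no figure for this point, so there is none to reproduce. The check has three parts.

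**1. Consistency of the definition.** Sections 8.2.2.1, 8.2.4 and 8.7.2.5.2 give the same window of one year up to and including the index date. The reading of the stratum is therefore not in doubt.

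**2. How many patients could be misplaced (illustration).**

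Inputs from Section 6.3, per 1000 person-years: acute MI 1.83, ischemic stroke 5.13, hemorrhagic stroke 1.00. Sum: 7.96.

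Assumptions: this rate is constant over Y prior years, all patients survive to index, and a share c of patients with only older events carries another listed code in the baseline year. The documents give neither Y nor c.

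- Event in the last year: 1 - exp(-0.00796) = 0.0079.
- Event within 5 years: 1 - exp(-0.0398) = 0.0390. Older only: 0.0390 - 0.0079 = 0.0311.
- Event within 10 years: 1 - exp(-0.0796) = 0.0765. Older only: 0.0765 - 0.0079 = 0.0686.

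Misplaced share of the no-history stratum = older × (1 - c) / (1 - last year - older × c).

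| c | Y = 5 | Y = 10 |
|---|---|---|
| 0 | 3.1% | 6.9% |
| 0.50 | 1.6% | 3.6% |
| 0.75 | 0.8% | 1.8% |
| 0.90 | 0.3% | 0.7% |

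For example, Y = 10 and c = 0.75 gives 0.0686 × 0.25 / (1 - 0.0079 - 0.0686 × 0.75) = 0.0172 / 0.9406 = 1.8%. The denominator leaves in patients who enter the history stratum through other items without any MI or stroke, so the true shares would be somewhat larger.

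**3. What the missing indicator could do to a risk ratio.** The formula in Section 8.9.1.4 gives

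RR_obs / RR_adj = (RR_CD × p1 + 1 - p1) / (RR_CD × p0 + 1 - p0),

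where p1 and p0 are the prevalences of an unrecorded older event in the two cohorts. All values here are assumed.

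- Equal prevalence: 1.00.
- 5% vs 3%: 1.05/1.03 = 1.02 at RR_CD = 2; 1.20/1.12 = 1.07 at RR_CD = 5.
- 5% vs 2%: 1.05/1.02 = 1.03 at RR_CD = 2; 1.20/1.08 = 1.11 at RR_CD = 5.

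For these inputs the factors are upper values, because they take the older event as wholly unmeasured; proxies in the propensity score would remove part of the bias.

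**The case against.** The best defence is that the definition is explicit, sits in the same sentence as the label, and applies one look-back to all cohorts. That is legitimate, and the fix keeps it. Four further points limit the concern.

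- **Other listed codes recapture some patients.** Myocardial ischemia, heart failure, angina, peripheral artery disease and other ischemic cerebrovascular events can all be coded in the year after an older MI or stroke. A reader might infer that most older cases are misplaced. That needs c below 0.5, and the documents do not give c.
- **Code content is not shown.** Appendix C lists codes for study drugs, migraine, acute migraine drugs and outcomes, but none for the baseline cardiovascular covariates. A listed label could already contain some chronic or history codes. The point rests on what the labels name.
- **Adjustment is incomplete, not absent.** A reader might infer that these patients go unadjusted. The descriptive step estimates "The naïve, unadjusted cumulative incidence of the outcome, R(t), subject to rightcensoring", so nobody is adjusted there, and 8.7.2.5.2 names no weights. In the gated comparison, Appendix D supplies drug and comorbidity proxies and allows common diagnoses to be added. The high-dimensional propensity score (8.7.2.5.3) screens diagnosis codes, and negative controls guard the comparison.
- **The stratum is secondary.** No objective in Section 7.1 targets it.

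These points reduce the size of the problem. None changes who is in the stratum: the optional additions and the high-dimensional score act on models, not on the stratum definition.

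**Conclusion.** The point holds as a mismatch between label and definition. Following the protocol as written, an MI or stroke more than 365 days before index, with no listed code in that year, counts as no history, and the comparison adjusts for it only through proxies. The share affected is unknown. Under the constant-rate illustration over 5 to 10 years, misplaced patients are about 3-7% of the no-history stratum with no recapture and about 0.8-1.8% with 75% recapture.

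Two numerical inferences should be avoided. First, 20,000 × 0.0079 gives about 160 erenumab users with an MI or stroke in the year, but that is not the size of the stratum, which has 22 components; the documents do not show that it is small. Second, the no-history risk is overstated by a factor of 1 + (k - 1) × misplaced share, where k is the risk in misplaced patients relative to the rest. At k = 10 with no recapture over 10 years this is 1 + 9 × 0.069 = 1.62. At k = 3 with 75% recapture it is 1 + 2 × 0.008 = 1.02 to 1 + 2 × 0.018 = 1.04. Both values of k are assumptions, so the large figure is a ceiling, not an estimate.

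This is an inexpensive improvement to a stated definition. It does not invalidate the study.

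**What to change.** In Section 8.7.2.5.2, Table 1 and Appendix D, add history codes recorded in the same 365 days: old MI, personal history of TIA or cerebral infarction, sequelae of cerebrovascular disease, and chronic ischemic heart disease. Where an existing label already contains some of them, say so. Count them as prior cardiovascular disease and include them in the treatment and censoring models. The look-back stays equal across cohorts and no new data are needed.

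In Section 8.9, state that cardiovascular history is limited to claims in the prior year, so an older event that left no claim in that year is still missed. If the codes are not added, the minimum is to rename the stratum as cardiovascular disease recorded in the past year.

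The cost is a few more diagnosis codes and a history stratum that mixes recent with older disease.

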# 8.7.3 Analysis of Safety Endpoint(s)/Outcome(s)

This study will estimate the risk of hypertension, stroke, and acute MI among individuals who are exposed to erenumab-aooe, other mAbs targeting the CGRP pathway (galcanezumab-gnlm, fremanezumab-vfrm, eptinezumab-jjmr), select SOC migraine preventive medications (anti-epileptics) (topiramate, valproic acid, divalproex sodium), and onabotulinumtoxinA. Hypertension, stroke and acute MI outcomes will be identified with ICD-10-CM codes.

# 8.8 Quality Control

The following list details the items that were considered or the actions that will be undertaken, as part of the specific quality assurance and data handling processes for this study:

• When customized cohorts are built for analyses, the level of QC will be determined as specified in Amgen MAN-002344.

- The Causal Studio SOP-431037 will be followed to ensure reproducible results.
- The study protocol, including analytic specifications, will be reviewed by the entire study team for overall clarity and validity of the study approach.
- The epidemiologist will check the distributions of enrollment data and sample data to ensure basic eligibility requirements are met. The epidemiologist will confirm that the distributions of age and index dates for the study cohorts are consistent with expectations. Cross-tabulation of variables included in final tables are reviewed for plausibility of results.
- The study team will review the preliminary and final output for consistency with expectations based on prior knowledge of the disease states.
- The epidemiologist will confirm that tables and content match the study protocol, that column percentages are computed accurately, and that tables are free of errors.
- Statistical programs and analytical data files produced to generate results will be archived for future reference.

### 8.9 Limitations of the Research Methods

### 8.9.1 Internal Validity of Study Design

### 8.9.1.1 Measurement Error/Misclassification

Measurement error may occur when identifying medication cohorts in claims databases because the presence of a claim for a prescription does not necessarily mean that the medication was taken as prescribed. Also, medication given as free samples by a physician will not be observed in claims data. For the current analyses, measurement error may also occur due to the free drug and coupon programs that have been available after launch of CGRP mAbs. Patient assistance programs are often sponsored by pharmaceutical companies to provide drugs at low or no cost to patients who lack prescription drug coverage for a particular medication. Using a different data source (not claims-based), it has been reported that 76% of the first 64439 new users of erenumab-aooe were covered through "discount/coupon" programs (Hines et al, 2019). Analyses using more recent data show that the majority of erenumab-aooe patients  $(\sim 60\%)$  continue to have coverage using this program. Similar programs have been in place for the other mAbs targeting the CGRP pathway. Although this will result in missing claims, it is not expected that this would introduce bias when assessing claims in relation to the outcomes under study. Care should be taken, however, to ensure that results are not interpreted as risk for the outcome in people who have newly started CGRP mAbs, but rather as risks in people who have a first claim in the database.

Patients who receive medical insurance from federal programs, such as Medicaid, are not eligible to receive additional financial assistance (through the Aimovig™ Ally Card) for erenumab-aooe (with the exception of the Safety Net program for Medicare

recipients), as this is stipulated by the federal government. This restriction of not allowing patients on government-funded health care programs to receive any financial assistance applies to all pharmaceutical companies, and, thus, patients on other mAbs targeting the CGRP pathway through government-funded health programs would also not be eligible to receive any financial assistance. As a consequence, the Marketscan® Medicaid Database provides an opportunity to indirectly evaluate the impact of the free drug and coupon programs on estimating risk amongst commercially insured patients, albeit in a study population that is potentially sicker and with higher levels of comorbidities. Through December 2019, there were 3181 new users of erenumab-acoe and 1692 new users of other mAbs targeting the CGRP pathway in the Marketscan® Medicaid Database. The expected number of new users through the administrative end of the study (31 May 2020) is: erenuamb ~ 4000; other mAbs targeting the CGRP pathway ~2500. We will estimate the cumulative incidence (ie, risk) of hypertension in both of these cohorts. Given the relatively small cohort sizes, estimation of the risk of rare outcomes such as acute MI and stroke will not be feasible. Comparative analyses will not be undertaken in the Marketscan® Medicaid Database.

# 8.9.1.2 Information Bias

There is the potential for the selected SOC migraine preventive medications (anti-epileptics) cohort and the onabotulinumtoxinA cohort to take their index medication for an indication other than migraine. To ensure these cohort members are migraine patients, a combination of two migraine diagnosis codes and/or prescription orders for migraine treatments will be required in the 12-month baseline period.

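### The two-item migraine rule that Section 8.9.1.2 says is required for the anti-epileptic and onabotulinumtoxinA cohorts is only partly implemented: three of the six inclusion routes admit a patient on one claim.

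*Protocol*

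**What the plan says.** Section 8.9.1.2 (Information Bias) names a specific risk: members of the anti-epileptic and onabotulinumtoxinA cohorts may happen "to take their index medication for an indication other than migraine". It offers one safeguard for those two cohorts: "a combination of two migraine diagnosis codes and/or prescription orders for migraine treatments will be required in the 12-month baseline period". This is worded as a condition of entry.

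The migraine criterion in Section 8.2.2.1 is common to all four cohorts: "A diagnosis of migraine during the baseline period, based on one of the following criteria". Six alternatives follow. The first is "≥1 inpatient claim with a diagnosis of migraine". The second is a single outpatient evaluation and management claim from a neurologist. The third is at least one "claim for emergency room visit with a diagnosis of migraine". The fourth pairs an outpatient claim with a "pharmacy fill for a migraine-specific triptan or an ergotamine class medication within 365 days of each other". The fifth is two spaced outpatient claims, and the sixth is two spaced triptan or ergotamine fills.

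Section 8.2.2.2 sets exclusions by cohort, all of which concern drug use in the prior year. The migraine code table in Appendix C lists, for every code, one inpatient, one emergency room or two outpatient diagnoses, in any position.

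**The concern.** A reader of the limitations section would conclude that every anti-epileptic and onabotulinumtoxinA user has at least two pieces of migraine evidence in baseline. A programmer working from the inclusion criteria would build cohorts where that is untrue. A new topiramate or valproate user with one migraine code from one neurologist visit would enter, whatever the drug was prescribed for.

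Section 8.9.1.2 raises the wrong-indication risk for these two cohorts only, so any contamination would fall on the comparator side of two of the three planned contrasts. It would also enter the cumulative incidences of hypertension, acute MI and stroke reported for those cohorts. The final report would then describe a control that had not been applied. Because Sections 8.2.2.1 and 8.9.1.2 and Appendix C differ, cohort membership also depends on which of them is coded.

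**Working it through.** No figure in the Protocol depends on this point, so the check sets the rules side by side.

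**Step 1. Minimum evidence for each route in Section 8.2.2.1.**

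| Route | What is needed | Items | Meets 8.9.1.2? |
|---|---|---|---|
| 3a | one inpatient claim | 1 | no |
| 3b | one neurologist outpatient claim | 1 | no |
| 3c | one emergency room claim | 1 | no |
| 3d | one outpatient claim and one triptan or ergotamine fill | 2 | yes |
| 3e | two outpatient claims, 7 to 365 days apart | 2 | yes |
| 3f | two triptan or ergotamine fills, 7 to 365 days apart | 2 | yes |

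Any one route suffices, so the effective minimum is one item. Three of six routes bypass the stated requirement.

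**Step 2. Is the rule imposed elsewhere?** The eligibility summary in the Abstract asks only for a migraine diagnosis in baseline. The cohort-specific criteria in Section 8.2.2.2 add nothing on migraine evidence and exclude no other indication. Epilepsy or seizure appears as a 0/1 covariate in Table 1 and Appendix D, not as an exclusion. No section makes two items a condition of entry.

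**Step 3. Appendix C against Section 8.2.2.1.** One inpatient code agrees with 3a, one emergency room code with 3c, and two outpatient codes with 3e apart from the spacing. A single neurologist outpatient claim passes 3b but fails the outpatient standard in Appendix C.

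**Step 4. Could the index drug be the second item?** Sections 8.2.2.1 and 8.2.4 include the index date in baseline, and Table 1 lists topiramate, valproic acid, divalproex and onabotulinumtoxinA among preventive migraine medications. Read literally, one migraine code plus the index claim could satisfy Section 8.9.1.2. That would make the prescription in doubt the evidence for its own indication, and the rule would protect against nothing.

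**Step 5. Which results are exposed?** Section 8.7.2.4 describes the first-stage cumulative incidences as naïve and unadjusted, so no covariate or weight acts on them. The contrasts with anti-epileptics and with onabotulinumtoxinA use weights built from Appendix D and run only if the comparability assessment allows.

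**Step 6. Size.** The Protocol gives neither the share of each comparator entering only through 3a to 3c, nor the share of those treated for another indication, nor their outcome risk. The effect cannot be computed.

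**The case against.** Section 8.9.1.2 sits among the limitations and may be a loose summary of the inclusion criteria; routes 3d to 3f are exactly combinations of codes and migraine prescriptions. The table in Appendix C has no field for specialty or fills, so its mismatch with 3b may be a matter of layout. Both observations are fair. They mean the safeguard is incomplete and the texts need aligning, not that no safeguard exists.

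There is also mitigation. Section 8.2.2.2 removes anyone who used one of the three anti-epileptics in the prior year, so established users for seizures are out. The treatment model in Appendix D includes epilepsy, cardiovascular and cerebrovascular history, prior preventives and utilisation, and Section 8.7.2.5.3 adds a high-dimensional propensity score. A contrast proceeds only after balance and negative-control checks. Section 8.3.4 reports that a similar migraine algorithm had high specificity and low sensitivity, although it says the study's own algorithm is unvalidated, and Section 8.9.3 warns that a single code may be miscoded or a rule-out. This mitigation stands for the comparative analyses. It does not reach the unadjusted descriptive risks.

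A reader might infer a material bias in the risk ratios. For a wrong-indication share f at k times the risk, a true ratio of 1 is estimated as 1/(1 + f(k − 1)). Assuming f = 0.05 and k = 2 gives 1/1.05 = 0.95; f = 0.20 and k = 4 gives 1/1.60 = 0.63. The documents do not support that reading. Neither input appears in them. The result is crude, whereas the 0.91 to 1.10 band in Section 8.7.2.4 concerns bias left after adjustment, and 0.95 lies inside that band anyway. The calculation also treats single-claim entry as the whole source of wrong-indication use, but an epilepsy patient with two migraine codes would still enter under a two-item rule.

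**Conclusion.** The inconsistency is real: Section 8.9.1.2 claims a requirement that the entry criteria enforce on three of six routes and not on the other three. Patients with one migraine claim, some of them possibly treated for another indication, can enter the two comparators the rule was meant to protect. This rests on the text alone and needs no assumption about magnitude.

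The size of any resulting bias is unknown. It is reduced, to an extent the documents do not show, in the two contrasts, and not at all in the unadjusted descriptive risks. It would go too far to say that the safeguard does not exist, that the risk ratios are biased beyond the Protocol's tolerance, or that a two-item rule would remove wrong-indication use. Two items confirm migraine; they do not show why the index drug was given. The point should be corrected before the cohorts are built, but it does not undermine the design.

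**What to change.** Reconcile Sections 8.2.2.1 and 8.9.1.2 and Appendix C, including the treatment of a single neurologist claim, in one of two ways.

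1. Add the two-item rule to the entry criteria of the anti-epileptic and onabotulinumtoxinA cohorts, and state that the index drug claim is not one of the items.
2. Keep 3a to 3c and correct the assurance in Section 8.9.1.2. Then, as a sensitivity analysis, repeat the descriptive risks and the erenumab contrasts with anti-epileptics and with onabotulinumtoxinA, excluding patients who qualified only on a single claim. Apply the same restriction to the erenumab arm there, so that the arms stay alike.

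Under either option, state in Section 8.9.1.2 that two items confirm migraine but not the indication of the index drug. Requiring two items in all four cohorts for the main analysis would be a design preference beyond what Section 8.9.1.2 promises, and is not needed to resolve the contradiction.

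The cost is protocol wording and one cohort filter. The second option gives somewhat smaller cohorts in the sensitivity analysis only. The first shrinks the two comparators themselves and leaves them with a stricter migraine definition than the erenumab cohort, which the report should say.
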